3.4.2 Sample Size for Prospective Study Phase

(1) Sample Size for Prospective Observational Validation ($n = 1,000$)

Estimation Basis: This phase evaluates the correlation strength between model predictions and real clinical prognosis (C-index) using sample size formulas for survival analysis. Relapse-Free Survival (RFS) is taken as the primary endpoint.

Assuming the 12-month RFS rate of the control group is 60% and the corresponding HR of the model-consistent group is 0.7, a total of 256 events are expected. Simulated by PASS 2021 software, more than 300 events can be observed in 1,000 cases within a 24-month study period (12 months for enrollment + 12 months for follow-up), which meets the requirements of statistical power and supports stratified analysis.

(2) Sample Size for Prospective Interventional Study

Estimation Basis: This phase is a Randomized Controlled Trial (RCT) with strictly calculated sample size, taking RFS as the primary endpoint.

Sample size formula for Log-Rank test is adopted with the following parameter settings: Baseline event rate: The 12-month RFS rate of the standard treatment group (Arm B) is 65%. Effect size: The 12-month RFS rate of the AI-assisted decision-making group (Arm A) is increased by an absolute value of 10% (up to 75%), corresponding to $HR = 0.67$. Significance level (α): 0.05. Statistical power ($1-\beta$): 80% (conventional standard for RCT). Accrual time: 18 months. Follow-up time: 12 months. Dropout rate: 10%.

Calculated by PASS 2021 software, a total of 200 events are required. Considering the dropout rate, the total required sample size is 600 cases (300 cases in each group). This sample size can detect the clinical difference corresponding to $HR = 0.67$ and meet the power requirements under follow-up and dropout conditions.

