Data governance organizational structure: A data governance committee is set up to formulate data management policies. Dedicated data administrators are assigned to be responsible for daily data management. A data quality supervision team conducts regular data quality inspections. All researchers are required to receive and pass data management training to ensure the implementation of standardized data management.

3.7 Adverse Events (Specific Definition, Classification, Reporting Methods and Treatment Measures for Adverse Events/Serious Adverse Events)

Adverse events in this study refer to any negative medical outcomes related to AI-assisted decision-making, which are divided into three grades:

Grade 1 (Mild): AI recommendations lead to minor inconvenience or reversible additional examinations without long-term impacts;

Grade 2 (Moderate): AI recommendations result in inappropriate treatment regimens, which require medical intervention for correction without permanent damage;

Grade 3 (Severe): AI recommendations lead to misdiagnosis and mistreatment, causing permanent functional damage or significant shortening of survival time.

Once an adverse event occurs, the clinical center shall report it to the research safety monitoring committee through the online system within 24 hours. The committee consists of experts in hepatology, oncology, pathology and medical ethics. Treatment measures include immediately suspending the use of the AI system, organizing experts to assess the cause of the event, determining the correlation with the AI system, and formulating corrective measures. All adverse events will be fully recorded and included in the final research report.

3.8 Statistical Analysis Plan (Methods for Missing Data Processing, Definition and Selection of Statistical Analysis Datasets, Statistical Methods for Comparing Primary and Secondary Outcome Indicators, Algorithm Stability Evaluation)

R (Version 4.2.0), Python (Version 3.9) and SPSS (Version 26.0) software will be used for all statistical analyses. All statistical tests are two-sided with a significance level of $\alpha=0.05$.

Missing data processing: Multiple imputation method is adopted. For continuous variables, the Multiple Imputation by Chained Equations (MICE) is used to create 5 imputed datasets for combined analysis. Mode imputation is applied for categorical variables. The missing data mechanism will be tested: Complete Case Analysis is adopted for data Missing Completely at

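### The RCT's 600 patients do not follow from its 200 events, and its assumed effect (75% RFS, HR 0.67) is not reconciled with the observational phase's 60% and HR 0.70

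*Protocol*

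**What the plan says.** Everything at issue is in Protocol Section 3.4.2, with the design taken from Section 3.1.

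**Randomised phase.** The method is given as "Sample size formula for Log-Rank test is adopted with the following parameter settings". The control assumption is "The 12-month RFS rate of the standard treatment group (Arm B) is 65" per cent; for the AI arm, "The 12-month RFS rate of the AI-assisted decision-making group (Arm A) is increased by an absolute value of 10% (up to 75" per cent), "corresponding to $HR = 0.67". The error rate is "Significance level (α): 0.05", and Section 3.8 adds "All statistical tests are two-sided with a significance level of" 0.05. Power is 80%, accrual 18 months, follow-up 12 months and dropout 10%. The stated results are 200 events and then "Considering the dropout rate, the total required sample size is 600 cases (300 cases in each group").

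**Observational phase.** The assumption is that "the 12-month RFS rate of the control group is 60% and the corresponding HR of the model-consistent group is 0.7". The study period there is 24 months, made up of 12 months' enrolment and 12 months' follow-up. Section 3.1 defines two cohorts in this phase: patients whose actual treatment agreed with the model and patients whose treatment did not.

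**Nature of the intervention.** Section 3.1 makes it advisory: physicians in the AI arm plan treatment with the model's recommendation before them, and controls receive routine care. Section 3.3 lists the decision change rate and physician adherence as secondary endpoints. Neither quantity enters the sample size.

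**The concern.** There are two separate problems.

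1. **From events to patients.** The event count depends on the HR, alpha and power. The patient count depends also on accrual, follow-up and dropout. All of these are stated, so 600 should be recoverable, and it is not. The two natural readings of 12 months' follow-up fall on opposite sides of 600, so a reader cannot tell whether the trial is generous or short, or when the primary analysis will take place.

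2. **Size of the effect.** The observational contrast is model-consistent against model-inconsistent treatment. The randomised contrast is advice against usual care, and it should be the weaker of the two wherever some usual-care decisions already match the model or some advice is not followed. The plan nevertheless assumes the larger effect for the randomised contrast (0.67 against 0.70). This is the programme's only randomised comparison, so its power should rest on an assumption that agrees with the paragraph above it or is defended against it.

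**Working it through.** **Events (the plan's figure reproduces).** HR = ln 0.75 / ln 0.65 = 0.668. With two-sided alpha 0.05 and 80% power:
- Schoenfeld: 4 × (1.960 + 0.842)² / (ln 0.67)² = 196.
- Freedman: (1.960 + 0.842)² × (1.67/0.33)² = about 201.
- Power at 200 events: Φ(√200/2 × |ln 0.67| − 1.96) = 80.8%.

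**Patients (the plan's figure does not reproduce).** Assume exponential RFS with λ = −ln(S₁₂)/12, uniform accrual, and dropout handled by dividing N by 0.9.

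*Reading A: 18 months' accrual, then 12 months after last entry.* Follow-up runs from 12 to 30 months, and P(event) = 1 − (e^(−12λ) − e^(−30λ))/(18λ).
- Control: 1 − (0.650 − 0.341)/0.646 = 0.521.
- AI arm: 1 − (0.750 − 0.487)/0.432 = 0.391.
- Mean: 0.456.

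*Reading B: 12 months for each patient.* P(event) is 0.35 and 0.25, mean 0.30.

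| | Reading A | Reading B |
|---|---|---|
| N for 200 events | 200/0.456 = 439 | 200/0.30 = 667 |
| N with 10% dropout | 488 | 741 |
| Events from 600 (540 after dropout) | 540 × 0.456 = 246 | 540 × 0.30 = 162 |
| Power at HR 0.67 | 88% | 72% |

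Under Reading B, 600 patients with no dropout at all would still give only 600 × 0.30 = 180 events. Two other routes also miss 600: exponential loss of 10% per year under Reading A gives 477, and a two-proportion formula gives 658 before dropout.

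**Cross-check of the effect.** Take the observational control group to be the model-inconsistent cohort.
- Model-consistent 12-month RFS: 0.60^0.7 = 69.9%, below 75%.
- Share of usual care already consistent if controls are at 65%: (0.65 − 0.60)/(0.699 − 0.60) = about 50%.
- HR with every AI-arm patient treated consistently: ln 0.699 / ln 0.65 = 0.83.

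Now vary control-arm concordance q. Controls have RFS 0.60(1 − q) + 0.699q, the AI arm is at 69.9% (full adherence), and expected events are for 540 patients under Reading A.

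| q | HR | Power at 200 events | Expected events | Power at those events |
|---|---|---|---|---|
| 0% | 0.70 | 71% | 281 | 85% |
| 25% | 0.76 | 49% | 273 | 62% |
| 50% | 0.83 | 26% | 265 | 33% |
| 75% | 0.91 | 10% | 256 | 12% |

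Holding controls at 65% instead and letting the inconsistent-patient rate move gives nearly the same HRs. At q = 0 it gives 250 events and about 80.5% power. Incomplete adherence lowers power further. With controls at 65% and 90% of the AI arm treated consistently, AI-arm RFS is 0.1 × 0.60 + 0.9 × 0.699 = 68.9%, HR 0.86, and power at 200 events is 18%.

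**The case against.** **The phases need not share assumptions.** Section 3.4 says the basis of the estimates varies by phase. The centre sets differ (10 to 15 against 3 to 5), as do the baselines (60% against 65%). The observational paragraph does not define its control group; equating it with the inconsistent cohort is an inference from Section 3.1. The observational HR is a non-randomised contrast that confounding could bias in either direction, and a design effect can be a detection target and not a forecast. All of this stands. It makes the second part an unexplained inconsistency between phases and not an arithmetical contradiction. It does not supply the missing justification: if HR 0.70 is causal, no baseline rate brings the randomised HR below 0.70.

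**A reader might infer that the trial's power is 26% and not 80%.** The document does not support that. At the RCT's own HR and 200 events, power is 80.8%. The 26% needs a shared population, a causal HR of 0.70, about 50% concordance, full adherence and analysis at exactly 200 events. Nor does power fall short in every case: at zero concordance, 600 patients under Reading A reach 80% to 85%.

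**A reader might infer that 600 is too few.** The observational paragraph's split of its study period into enrolment plus follow-up favours Reading A, under which 600 is a surplus. Only Reading B makes it short. The objection therefore settles the likely direction, but not the missing derivation.

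**A reader might infer that a null result could not be interpreted.** That goes too far, because decision change and adherence are already secondary endpoints in Section 3.3.

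**Conclusion.** The point holds in two parts.

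1. **The stated sample size is not derivable from its inputs.** The 200 events are correct for HR 0.67. The patient count that goes with them is about 488 or about 741, depending on the meaning of follow-up, and 600 is neither. On the likelier reading the discrepancy is on the safe side (about 246 events, 88% power at HR 0.67). On the other, 600 gives about 162 events and 72%. This rests on exponential RFS, uniform accrual and the stated 10% dropout.

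2. **The effect assumption is not reconciled with the observational paragraph.** Taken together, the two paragraphs require an advisory intervention to do better than fully model-consistent treatment. If the phases are comparable and HR 0.70 is causal, power depends mainly on a concordance figure that the protocol does not give, and over 0% to 75% concordance it runs from about 85% to 12% at the planned enrolment under Reading A. The 26% is one conditional scenario within this exercise, not the design's power.

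**What to change.** In Section 3.4.2, for the randomised phase:

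- State whether follow-up is 12 months per patient or 12 months after the last patient enters.
- State the number of RFS events that triggers the primary analysis.
- Restate N, expected events and power from those choices. If 600 is kept, give its own expected events and power (about 246 and 88% at HR 0.67 under Reading A), and stop describing 600 as the number required for 200 events.
- Use one set of RFS rates and effects across the two prospective phases, or justify the difference, and say who the observational control group is.
- Report RCT power as a function of control-arm concordance and AI-arm adherence, and update it with the concordance measured in the observational cohort, which that phase already records.

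The cost is a revised sample-size paragraph and a short power table, with no new data collection. The stated power may become less favourable, or enrolment may need to be reconsidered once concordance is known.

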3.5 Bias Control and Fairness

A multi-level and systematic strategy is adopted to strictly control various potential biases in the study and ensure the scientificity and reliability of research results.

Bias control in study design phase: Standardized inclusion and exclusion criteria are formulated to control selection bias. In multi-center studies, all centers are required to adopt a unified patient screening process. Selection bias is assessed by comparing the basic characteristics of enrolled and unenrolled patients. For the prospective interventional study, central randomization (block randomization stratified by center) is used to assign patients to the AI-assisted decision-making group or standard treatment group to ensure balanced baseline characteristics between groups.

Bias control in data collection and processing phase: Strict blinding principles are implemented to reduce information bias and measurement bias. For pathological image annotation, at least two senior pathologists conduct independent annotations without access to any clinical outcomes of patients, and discrepancies are arbitrated by a third expert to establish high-quality gold standards. During model development, algorithm developers are prohibited from accessing data of subsequent validation sets to avoid overfitting caused by manual tuning. An independent clinical endpoint adjudication committee is established in the endpoint evaluation phase. Committee members are blinded to patient grouping information and AI prediction results, and judge tumor recurrence and survival events objectively according to established criteria to minimize assessment bias.

Bias control in algorithm development and validation phase for AI-specific biases: For spectrum bias, slide images scanned by different devices and stained with different procedures from multiple medical centers are collected. Color normalization techniques (such as the Macenko method) are adopted in the preprocessing phase to reduce the impact of staining differences. Multi-center and large-sample external validation is conducted to evaluate and correct the performance differences of the model across different populations and devices so as to control measurement bias. In addition to dividing independent validation sets, regularization and Dropout technologies are applied to prevent overfitting. Cross-validation and Bootstrap sampling results are used when evaluating model performance.

Fairness assessment: Comprehensive fairness evaluation is carried out to analyze whether there are significant differences in model performance across subgroups divided by demographic characteristics (gender, age) and clinical characteristics (tumor stage, etiology, liver function classification). Core evaluation indicators include inter-group AUC difference, balanced odds and fairness metrics for sensitive attributes. If performance discrimination of the model is found in specific subgroups, algorithm correction will be performed to ensure the fairness of algorithm decisions. All fairness evaluation results will be fully disclosed in the research report.

Bias control in statistical analysis phase: Multivariate Cox regression model and Logistic regression model are used to adjust for known prognostic factors (such as TNM stage, vascular invasion and AFP level) to accurately estimate the independent predictive efficacy of the AI model and control potential residual confounding bias.

3.6 Data Governance System (Data Collection, Transmission, Storage Security Control; Full-chain Data Recording)

A sound data governance system is established to ensure the quality, security and compliance of data throughout the research process, covering all links including data collection, transmission, storage, processing, analysis and archiving, forming a complete data management closed loop.

Standardized data collection: Detailed Standard Operating Procedures (SOPs) for data collection are formulated to clarify the definition, format and collection specifications of all types of data. Structured electronic Case Report Forms (eCRFs) are used for clinical data collection with built-in logic verification and range check functions to ensure the accuracy and completeness of data collection. Pathological image data collection follows digital scanning standards with a unified scanning resolution of 0.25 μ m/pixel and file format of SVS. Equipment calibration and quality control tests are conducted before each batch of scanning. Laboratory test data are directly collected by docking with the Laboratory Information System (LIS) to avoid manual transcription errors.

Security control for data transmission: End-to-end encryption technology and TLS 1.3 protocol are adopted for all data transmission to secure the transmission channel. A complete data transmission log system is established to record the transmission time, content, sender and receiver. Desensitization is performed on data before cross-institutional transmission: direct identifiers are removed and indirect identifiers are generalized. Data integrity verification and digital signature technology are applied during transmission to prevent data tampering.

Data storage management: A hierarchical storage strategy is implemented. Raw data are stored on internal servers of each institution with physical isolation and access control. Analytical data are stored on a dedicated research platform with encrypted storage technology. A complete data backup and recovery mechanism is established: incremental backup is performed daily and full

backup is performed weekly, with backup data stored off-site. The data storage system has passed ISO 27001 certification, and regular security vulnerability scanning and penetration testing are carried out.

Quality control in data processing: A comprehensive data quality evaluation indicator system covering integrity, accuracy, consistency and timeliness is established. Automated data quality inspection tools are used for regular data quality assessment. Once data quality problems are identified, root cause analysis is conducted and corrective and preventive actions are implemented. A complete audit log is recorded for all data processing operations to ensure traceability.

Data archiving and destruction: All research data are archived in accordance with standard specifications after the completion of the study, including raw data, processed data and final analysis data. A strict data access permission management system is established to control the scope of data use. Physical destruction or multiple overwriting technologies are adopted for data destruction to ensure data is irrecoverable. Detailed records are kept throughout the archiving and destruction process.

Data governance organizational structure: A data governance committee is set up to formulate data management policies. Dedicated data administrators are assigned to be responsible for daily data management. A data quality supervision team conducts regular data quality inspections. All researchers are required to receive and pass data management training to ensure the implementation of standardized data management.

3.7 Adverse Events (Specific Definition, Classification, Reporting Methods and Treatment Measures for Adverse Events/Serious Adverse Events)

Adverse events in this study refer to any negative medical outcomes related to AI-assisted decision-making, which are divided into three grades:

Grade 1 (Mild): AI recommendations lead to minor inconvenience or reversible additional examinations without long-term impacts;

Grade 2 (Moderate): AI recommendations result in inappropriate treatment regimens, which require medical intervention for correction without permanent damage;

Grade 3 (Severe): AI recommendations lead to misdiagnosis and mistreatment, causing permanent functional damage or significant shortening of survival time.

Once an adverse event occurs, the clinical center shall report it to the research safety monitoring committee through the online system within 24 hours. The committee consists of experts in hepatology, oncology, pathology and medical ethics. Treatment measures include immediately suspending the use of the AI system, organizing experts to assess the cause of the event, determining the correlation with the AI system, and formulating corrective measures. All adverse events will be fully recorded and included in the final research report.

3.8 Statistical Analysis Plan (Methods for Missing Data Processing, Definition and Selection of Statistical Analysis Datasets, Statistical Methods for Comparing Primary and Secondary Outcome Indicators, Algorithm Stability Evaluation)

R (Version 4.2.0), Python (Version 3.9) and SPSS (Version 26.0) software will be used for all statistical analyses. All statistical tests are two-sided with a significance level of $\alpha=0.05$.

Missing data processing: Multiple imputation method is adopted. For continuous variables, the Multiple Imputation by Chained Equations (MICE) is used to create 5 imputed datasets for combined analysis. Mode imputation is applied for categorical variables. The missing data mechanism will be tested: Complete Case Analysis is adopted for data Missing Completely at

Random (MCAR); multiple imputation is used for data Missing at Random (MAR); selection models are applied for data Missing Not at Random (MNAR). Sensitivity analysis is conducted to compare results obtained by different missing data processing methods.

Definition of statistical analysis datasets:

Full Analysis Set (FAS): Includes all randomized patients who received at least one efficacy assessment, analyzed according to the Intention-To-Treat (ITT) principle.

Per-Protocol Set (PPS): Includes patients who fully complied with the research protocol, excluding patients with major protocol violations.

Safety Set (SS): Includes all patients who received at least one treatment, used for safety evaluation.

Primary analysis is based on the FAS, and the PPS is used for sensitivity analysis to verify the robustness of results.

Statistical methods for primary outcome indicators: For categorical variables (such as treatment response grouping), weighted F1-score and macro-average AUC are taken as main evaluation indicators, and Cohen's Kappa coefficient is used to assess the consistency between model predictions and actual clinical conditions. For survival data (RFS and OS), the Kaplan-Meier method is used to draw survival curves, the Log-rank test is used for inter-group comparison, and the Cox proportional hazards regression model is established to calculate the Hazard Ratio (HR) and its 95% confidence interval while adjusting for potential confounding factors such as age, gender and TNM stage.

Statistical methods for secondary outcome indicators: Decision Curve Analysis (DCA) is used to evaluate the clinical net benefit of the model. Calibration Curve and Brier Score are used to assess the accuracy of predicted probabilities. Repeated-measures Analysis of Variance is used for inter-group comparison of continuous variables. The Mann-Whitney U test is adopted for ordinal variables such as physician adherence and decision confidence scale scores.

Algorithm stability evaluation: Bootstrap sampling (1,000 repetitions) is used to calculate the 95% confidence interval of model performance indicators for stability assessment. SHapley Additive exPlanations (SHAP) values are used to analyze feature importance and improve model interpretability. Intraclass Correlation Coefficient (ICC) is calculated to evaluate the consistency of the model across different centers; $ICC > 0.75$ is regarded as good consistency.

Subgroup analysis and sensitivity analysis: Subgroup analysis is performed according to key clinical characteristics including age (≤ 60 years vs > 60 years), gender, TNM stage (Stage I-II vs Stage III-IV) and degree of liver cirrhosis. Interaction test is used to evaluate subgroup differences. Sensitivity analysis is conducted by changing statistical model parameters and adopting different missing data processing methods to verify the robustness of research results.

Sample size re-estimation plan: If the deviation between the event rate of primary outcome indicators observed in interim analysis and the initial assumption exceeds 20%, the Lan-DeMets method combined with O'Brien-Fleming boundaries will be used for sample size re-estimation. Re-estimation is limited to once and must be approved by the Data Safety Monitoring Board (DSMB).

All statistical analyses are conducted in accordance with the pre-specified statistical analysis plan. All post-hoc analyses are clearly marked as exploratory. Point estimates and 95% confidence intervals are reported for all statistical results, and p-values are retained to three decimal places. Conclusions will not be drawn based solely on p-values.

3.9 Full-process Quality Control of Project Data (Data Entry, Coding and Storage Methods, Measures to Improve Data Quality; Measures to Ensure Subject Compliance in Clinical Observation and Follow-up; Measures to Ensure Consistency Across Multi-center Studies)

A comprehensive and systematic data quality management system is established covering the whole process of data collection, transmission, storage, processing and analysis to ensure the integrity, accuracy, consistency and reliability of research data.

Quality control for data collection: Unified Standard Operating Procedures (SOPs) for data collection are formulated to clarify the definition, collection time and recording standards of all observation indicators. An Electronic Data Capture (EDC) system is used for data entry with built-in logic verification and range check functions to identify abnormal values and inconsistent data in real time. Dual independent data entry is adopted for clinical data, and discrepancies are verified against original documents by a third party. Pathological image data collection follows standardized procedures. Calibrated scanning devices are used, and quality control tests are conducted before each batch of scanning to ensure consistent image resolution and color.

Security control for data transmission and storage: Encrypted protocols (SSL/TLS) are adopted for data transmission. A hierarchical management strategy is implemented for data storage: raw data are stored on internal servers of hospitals, and desensitized data for analysis are stored on a secure cloud platform. A complete data backup mechanism is established: incremental backup is performed daily and full backup is performed weekly, with backup data stored off-site. A complete log is recorded for all data operations to ensure traceability.

Data governance and multi-level quality audit mechanism: A data quality management team is set up to conduct regular random inspections on data quality and generate monthly data quality reports. A data quality evaluation indicator system including data completeness rate, consistency rate and timeliness rate is established. Root cause analysis and Corrective and Preventive Actions (CAPA) are implemented once data quality problems are identified. The entire data cleaning process is fully recorded with all data modification traces retained.

Quality control for clinical observation and follow-up: Detailed SOPs for clinical observation and follow-up are formulated to unify observation indicators, measurement methods and recording standards. An electronic follow-up system is applied to automatically remind follow-up time points and reduce the loss to follow-up rate. Regular training and quality assessment are conducted for researchers to ensure standardized operations. An endpoint event adjudication committee is established to judge tumor recurrence and survival status in a blinded manner uniformly and ensure the objectivity of endpoint data.

Quality control for multi-center studies: Unified training is organized for researchers from all centers before the study starts to ensure consistent understanding of the research protocol. A centralized monitoring plan is formulated with regular on-site and remote monitoring. Standardized data collection tools and unified data definitions are used to ensure data consistency across all centers. Regular coordination meetings are held to solve problems encountered in data collection in a timely manner. Centralized random audit is implemented to ensure the consistent implementation of the research protocol in all centers.

Data security management: A data classification and grading management system is established, and encrypted storage and strict access control are implemented for sensitive data. All researchers receive data security and privacy protection training and sign confidentiality agreements. Regular

security vulnerability scanning and risk assessment are carried out to eliminate potential security hazards. A data security emergency response plan is formulated with a corresponding emergency response mechanism.

The above comprehensive and systematic quality control measures ensure the authenticity, accuracy and integrity of research data and provide a solid guarantee for the reliability of research conclusions. All quality control activities are fully recorded to form a complete quality assurance document system.

